A Statistical Analysis Plan (SAP) will be created before the database locks. A blinding review of the data will focus primarily on issues related to the exclusion of patient or patient data from missing and analyzed data.

The subjects to be validated for the data obtained from the subjects of the clinical trial are

classified into the ITT (intention-to-treat) analysis group and the PP (per protocol) analysis target group.

- ITT analysis group consisted of all randomized subjects after satisfying the selection / exclusion criteria.
- The subjects who underwent the PP analysis were those who completed the clinical trials of the ITT target group, and observed the primary efficacy variables as planned without violating the critical clinical trial plan. Completion of the clinical trial is defined as discharge following normal procedure without further hospitalization after surgery. Critical clinical trial protocol violations include:
 - · Violation of selection / exclusion criteria
 - · Random assignment violations
 - Take medication for concomitant medication
 - In case of any other serious clinical trial protocol violation
- The analysis of the basic characteristics of the patients, including demographic data and clinical history data, is evaluated using the ITT analysis group. All of the validation variables were analyzed for the ITT group and the PP group. The results of the study on serum CRP at day 2 postoperatively were used as the main evaluation group.

Safe Safety evaluation variables such as adverse events and adverse reactions are analyzed using the safety analysis target group.

- The safety analysis group consisted of all subjects who underwent randomized placement.
- Statistical tests for all efficacy / safety parameters should be performed at the 5% significance level. If the data do not meet the assumptions needed to perform a parametric test, a non-parametric test such as the Wilcoson rank-sum test is performed.

A multivariable analysis of primary and primary secondary efficacy variables is performed. Multivariate analysis uses multiple linear regression models or multiple logistic regression models depending on the type of outcome variable. The main independent variable is the test, we will include the gender and stage of the stratified variables used in randomization in the model and the perturbed variables identified in the demographic and clinical history data analyzes to control the effect. For repeated measurement data, perform a multivariate analysis using the generalized estimation equation (GEE). If a significant interaction effect is found between the treatment group and the participating laboratories and / or the treatment group and the confounding variables, the effect is controlled by including the interaction term in the multivariate model.

• The content of the pre-planned subgroup analysis to be performed in this trial is as follows:

- Gender Male Female)
- BMI (<25 / ≥25)
- Cancer stage (TNM stage)
- Operator
- In vitro / Internal Anastomosis
- The differences between the groups were assessed using the Student's t-test (or the corresponding nonparametric Wilcoxon rank-sum test) or the χ2 test (or Fisher's exact test, the corresponding nonparametric method) Analysis. If control of disturbance variables is required, multivariate analysis is performed.

9-2) Treatment of missing values.

In general, the missing value will be treated as a missing state, and no alternative missing statistic is used. Therefore, only observations will be used for data analysis. Discrepancies data are replaced by missing values at the responsibility of the clinical trial manager.

10) Clinical trial and treatment standard

The same type of treatment and treatment will be given to patients with general gastric cancer who are being treated at Seoul National University Hospital.

11) Study Schedule

- 42 months after IRB approval: registration of clinical trial subjects and clinical trials
- 42 months ~ 48 months: Data analysis and presentation

12. Data and Safety Monitoring Plan

1) The person in charge of monitoring

- * Monitoring supervisor: [name], Associate Professor, Surgery, Seoul National University Hospital
- * Person in charge of monitoring: [name], Department of Nurse, Seoul National University Hospital

2) Data and safety information monitoring items

- * Study accruals item: all items in the case record of the clinical trial subject being monitored
- * Safety items: adverse reactions (complications)

3) Data and safety monitoring method and cycle

Designated monitoring personnel shall be monitored to ensure the safety and data availability

of those who comply with the Clinical Trial Management Standards for Medicines (KGCP) and participate in clinical studies. The monitoring person will randomly select one person at the time of registration for the first clinical trial and every 20 people at the time of registration, confirm the completeness of the case record, clarity, check with the data base. Food and Drug Administration, Clinical Trials Review Committee, may be required to see evidence documents, case records, and other test documentation for inspection or surveillance by the implementing agency, the examiner accepts this and should always cooperate in this process.

4) Abnormal drug response report, non-compliance of study, report of unexpected problem

The researcher and the person in charge should ensure the safety of the subject. If the unexpected serious adverse reaction, serious research failure or unexpected problem occurs, the doctor or researcher who confirms it should report it immediately to the research director. The investigator reports to the IRB a report on serious adverse reactions within 15 working days of the researcher. Significant adverse events are the following adverse reactions that occur due to clinical trial medical devices:

- to cause death or life-threatening
- If you need to extend the period of hospitalization or hospitalization
- causing persistent or meaningful impairment or impairment
- If it causes birth defects or abnormalities
- Other important medical events

The tester shall record in the case record information on the date of occurrence, disappearance date, extent, treatment, progress, and the causal relationship with the clinical trial device. Whether or not there is a relation with the medical device for clinical trial is evaluated based on the following, and the opinion of the tester is described.

Clear Relevance

- If the timing of the use of the medical device for clinical testing and the appearance of the adverse reaction is reasonable
- If the adverse event is most likely explained by the medical device for clinical use for any other reason
- Disappearing due to discontinuation of medical devices for clinical trials
- Reuse (only if reusable) Results are positive
- If the adverse event is consistent with information already known to the clinical trial

2 Multi-related Relevance

- If there is evidence that a medical device for clinical trials has been used
- If the timing of the use of the medical device for clinical testing and the appearance of the adverse reaction is reasonable
- Adverse events are more likely to be explained by the use of medical devices for clinical use than for other reasons
- Disappearing due to discontinuation of medical devices for clinical trials

3 Suspected Relevance

- If there is evidence that a medical device for clinical trials has been used
- If the timing of the use of the medical device for clinical testing and the appearance of the adverse reaction is reasonable
- If the adverse events are judged to be due to the use of medical devices intended for clinical use at the same level as other possible causes
- Disappearance of medical devices for clinical trials (if implemented).

(4) Low related Relevance

- If there is evidence that a medical device for clinical trials has been used
- There are other possible causes of the adverse reaction
- If the result of discontinuing use of the medical device for clinical trials (if implemented) is negative or ambiguous
- Reuse of medical devices for clinical trials (if possible only) Results are voiceless or ambiguous

5 None Relevance

- If the subject does not use the medical device
- If the timing of the use of medical devices for clinical trials and the occurrence of adverse events is not feasible
- There are other obvious causes for adverse events

6 Unknown

• If information cannot be judged as insufficient or conflicting and cannot be supplemented

or verified

5) Study Abortion Criteria

Discontinuation of research or change of plans may be considered in the following cases.

- If the achievement of the target number of study subjects is expected to be delayed by more than one year from the original plan
- If a large number of unexpected serious adverse events occur in relation to a particular organization, determine whether to exclude studies from the study group or to the remaining groups

13. Measures to protect the safety of the subjects

1) Basic plan for securing ethics of research

This study will comply with the most recent Helsinki Declaration (revised in 2013) and the ICH-GCP, and implementation will begin after IRB approval. The types of surgical instruments used are not blindfolded. Researchers strive to minimize the effects of bias on the results of the research and strive to do their best to ensure the safety of the study subjects.

2) Consent process of the subject

In this study, the doctors included in the collaborators will explain the subject in detail of prescreening research in a language that can be understood by the general public. The description of the study will be performed at the ward at the time of admission to the outpatient clinic or surgery, and the explanatory text and the consent form will be provided to the subject so that they can decide whether to consent for a sufficient time. During the explanation and agreement acquisition process, the research will be voluntary and will attempt to minimize the likelihood of compulsory or unjustified impact by explaining that withdrawal is possible at any time and ensuring standard best practice, whether or not the research is agreed. Consent will be obtained by voluntarily signing the consent form with the subject of the clinical study, and a copy of the statement and agreement will be provided to the subject.

3) Compensation plan of subject

This study was conducted according to standard surgical methods using medical devices that are already widely used and approved, and there are no additional outpatient visits. Therefore, there is no financial compensation for participants participating in research.

As the Cytokine test is not included in routine medical care, the research cost will be charged. In the present study, the postoperative complications were predicted not to exceed the range of complications after general gastric cancer surgery. However, if unanticipated adverse events are considered to be directly related to participation in the study, the reimbursement will be made as prescribed in the insurance under the Clinical Study Subject Compensation Code.

4) Personal information protection plan of research subject

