Program used for calculation: PASS (Power Analysis and sample size software; http://www.ncss.com)

Calculation result of study subject number:

Croup	Gro	up 1	Group 2		Subject	Total subject	
Group Comparison Me	Maan	Standard	Maan	Standard	number of	number with 10%	
Companson	Mean	deviation	Mean	deviation	each group	omission rate	
A vs B	11.5	6.6	8.0	6.6	57	189	

^{*} Total subject number with 10% omission rate = subject number of each group / 0.9 * 3

The primary concern of this study is to compare ultrasonic shears (A) and advanced bipolar Sealing device (B). Hybrid instrument (C) is expected to have similar temperature from its operating features even though there is no previous trustworthy research. We have decided total of 189 target patients, same numbers in A and B in order to contrast balance weigh in equal condition.

4) Study subjects invitation plan

Invitation will be made to patients, satisfying selection/exemption criteria among those who are gastric cancer patient visiting Gastric Cancer Center in Seoul National University Hospital or hospitalized gastric cancer patient who requested gastric cancer treatment to the study research team. Invitation will be explained verbally, with a consent form.

11. Research method

1) Research method in detail

Under general anesthesia of the patient, satisfying selection/exemption criteria, the subject will be appointed to the each study group of 1:1:1 ratio and the surgery will only use an energy-based device of each selected group. The patients will be randomized using web-based program, which will be generated by medical research collaboration center (MRCC), Seoul National University Hospital. Institutes and the presence of incision during anastomosis (intracorporeal or extracorporeal anastomosis) will be the stratification factors during randomization. Blood loss, blood transfusion volume, operation time, cytokines and others will be measured during the operation and amount of drainage, laboratory test and adverse reaction will be post-operatively observed and accessed. Unless follow-up or extension of admission is needed due to the adverse reaction, patients will be discharged during the post-op 5-10 days. Follow-up will be made until the first out-patient visit after 2-3 weeks of discharge.

(1) Evaluation criteria during operation

① Blood loss during operation: Output-input.

The blood loss will be measured with sum of absorbed blood in gauzes and absorbed amount using inhalator.

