Absorbed blood in gauze: measure weight of the gauze before the operation then calculate the difference after the operation.

Absorbed amount of blood using inhalator: blood collected in the inhalator bottle will be moved to the 50cc syringe then the amount of blood will be measured. If saline is used for wash out operation region during the operation, that amount will be omitted.

- ② Operation time
- ③ Transfusion volume

(2) Pre- and Post- operation management

- i. Within a month from the date of operation: A laboratory test (CBC, admission panel, CRP, triglyceride, amylase, PT, aPTT), age, medical history, ASA classification, weight, height.
- ii. 1 day before operation: bowel preparation (empty stomach and enema): use of a laxative before operation (Mg. citrate powder intake, suppository bisacodyl 10mg) and suppository glycerin enema and bisacodyl 10mg on the day of operation.
- iii. low molecular weight heparin (LMWH): to prevent DVT, hypodermic medication of 20mg 1 time/ 1day may possible after 2 ~3 days post operatively.

(3) Post-operative evaluation

- PCA (patient controlled analgesia): includes Morphin and fentanyl. When need additional pain control, Nalbuphin (IM) or Fentanyl patch will be used
- 2 From POD 1 to 4, VAS pain score will be measured daily.
- 3 Gas out, day of starting liquid diet will be recorded
- ④ Complications: Within the follow-up period, from the end of operation to 2-3 weeks after discharge, patients will be monitored to check for complications and mortality before POD 30. Complications will be measured by Clavien-Dindo classification. Any reasons for re-admission through an out-patient clinic or emergency during the followup period will separately be recorded.

(4) Laboratory test

i. POD 2, 4: Blood test (CBC, admission panel, CRP, triglyceride, amylase)

ii. POD 2: Amylase and triglyceride test in the drain. Measurement of drainage by 1-3 days after surgery

iii. Cytokines Test:

- Serum IL-6, IL-10: Obtain peripheral blood in 5ml bottle of EDTA bottle : just after the induction of the anesthetia, 2-3 hours after the end of the operation, the 2nd post-operative day, and the 4th post-operative day.
- EDTA bottle is centrifuged at 3000 rpm for 15 minutes as soon as possible after collection. It is divided into 200ul each, and then cytokine assay is asked to clinical research laboratory. On holidays when it is difficult to conduct the test, it is centrifuged, stored at -80 °C and analyzed at the day available.

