- After the screening number was assigned, the subjects who satisfied all the inclusion criteria and were not eligible for any exclusion criterion were judged to be suitable for the study. After the insertion of the laparoscopic trocar under general anesthesia, (Eg, after a confirmation of unexpected intraperitoneal or severe adherence do not exist), randomization should be performed. A randomization number (patient ID) will be awarded in a strictly sequential manner in accordance with the randomization table generated by the medical statisticians in advance.
- The randomized method uses a centralized stratified block randomization method to ensure a balanced distribution among the three groups. Institutes and the presence of incision during anastomosis (intracorporeal or extracorporeal anastomosis) will be the stratification factors.
- If a clinical trial subject discontinues clinical trials, the random assignment number assigned to the subject will not be re-used and the subject will not be able to participate in the trial again.
- The trial will be conducted with a single blind spot. Therefore, the practitioner knows the contents of the randomization, but does not disclose the contents of the clinical trial subjects for about 4 weeks after the end of the clinical study.

3) How to use test medical device, combination therapy, reasons for selection when using treatments

Energy-based devices are used in accordance with the manufacturer's manual and the commonly used principles of laparoscopic surgery, and the sites of use during surgery are as described in above 9-1)-(2).

4) Observation items, clinical examination items and observational examination methods

- (1) Primary endpoint: Serum C-reactive protein (CRP) at POD 2
- (2) Secondary endpoint:
 - Blood loss during operation, amount of blood transfusion

- IL-6, IL-10 in serum and ascites at 2-3 hours after surgery and POD 2, 4
- Complication within 30 days after surgery, mortality rate
- At 4 days postoperatively, serum CRP
- Postoperative visual pain score (VAS score)
- The timing of gas release after surgery, start time of liquid diet
- Length of stay, re-admission, emergency room visit and reasons
- Amount of drainage after surgery
- Concentration of triglyceride and amylase in drain
- Amount of Indocyanine green in the peritoneal cavity after surgery, which is injected submucosally before dissection (only in Seoul National University Hospital)
- Number of resected lymph nodes

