item Pre-Op (Baseline			Intra-		PC	DD (Post	Operativ	1st outpatient visit after discharge	End of study/ Early termination		
	(Baseline)	abdomen	Ор	2-3hr	#1	#2	#3	#4	Discharge		
Informed consent ¹	✓										
Selection/exclusion criteria	√										
Demographic information	✓										
History, ASA	✓										✓
Physical examination, weight	*										√
Random assignment		✓									
Lab (cbc, admission panel, amylase, CRP², triglyceride³)	*					*		✓		(✔)	
Blood cytokine ⁴		✓		*		1		1			
JP drain amount					1	1	1				
JP drain TG, amylase						1					
ICG concentration ⁵			✓								
Operation ⁶											
Blood volume			✓								✓
Operation time			✓								✓
Amount of blood transfusion			✓								✓
Surgical information			✓								✓
Analgesic medication (excluding PCA)					√	✓	*	√			
VAS pain score	*				1	✓	1	1			
Gas out day									✓		
Soft diet starting date									✓		
EGD, EUS,CT	✓										
Hospital stay count									✓		✓
Pathologic result confirmation	1								✓	*	
Adverse events ⁷			✓	✓	*	√	✓	✓	*	1	✓
Follow-up visit		_								1	

All procedures, including selection / exclusion criteria, may be initiated after voluntary written consent has been obtained from the subject. If surgery is not performed within thirty days after obtaining the consent form, the procedures for rehabilitation shall be carried out.

CRP was further examined within 2 days before surgery

Triglyceride is examined by the researcher's option on the first outpatient visit after discharge

After patient anesthesia in the surgical field, blood is drawn through the A-line.

Only for Seoul National University Hospital

Surgery is performed according to standard surgical guidelines.
 Adverse events are evaluated up to POD # 30.

4-1) Baseline before surgery

- 1) Subject consent form
- 2) Demographic information
- 3) Detailed medical history
- 4) Significant medication or operation history
- 5) Physical examincation
- 6) Laboratory test: CBC, PT, aPTT, BUN, Triglyceride, Albumin, Total bilirubin, Creatinine, CRP, Amylase, use the test results within 30 days before surgery
- 7) Concomitant medication (including drugs within the past week)
- 8) EGD, EUS, CT use test results within 2 months from the scheduled date of surgery.
- 9) Measure VAS score on the day before surgery.

4-2) operation day

- 1) Randomization: prior to surgery.

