- 2) Operation method: Lymph node dissection range (D1+) and removed lymph node area, mating method, etc. are recorded; and the ablation range is left as a photograph.
- 3) Volume of blood loss
- 4) Operation time
- 5) Volume of blood transfusion
- 6) Cytokine test: as described in 11-1)-(4)
- 7) ICG measure: as described in 11-1)-(5)
- 8) Adverse reaction

4-3) POD 1 ~ discharge date

- 1) Amount of drainage: measured in 24 hour unit
- 2) Number of lymph nodes removed
- 3) Amount of blood transfusion
- 4) Adverse reaction
- 5) Laboratory test (POD 2, 4): serum CBC, admission panel, CRP, triglyceride, amylase, IL-6 and IL-10
- 6) Triglyceride and amylase from JP drain (POD 2)
- 7) Date of gas out and initiation of soft diet
- 8) Complications

4-4) Follow-up: first outpatient visit after discharge (3-4 weeks after surgery)

- 1) Adverse reaction
- 2) Complications
- 3) Re-admission or emergency visit record and reason

4-5) unscheduled evaluation and early termination:

- If an evaluation of the subject is performed at an unscheduled point of time, record the evaluation items such as adverse reactions, dropouts, clinical measurement results, and medical treatment.
- For those patients who have dropped out, the evaluation items should be measured at the time of withdrawal.

5) Differentiation from existing treatments and research

Many of the existing studies comparing energy-based devices have been performed in laboratories; so there has been a limit to assessing the effects of surgery on patients. The purpose of this study was to evaluate the effect of each surgical instrument on the patients in stomach cancer surgery, especially for lymphadenectomy and hemostasis.

6) Benefits and risks of the subject

The energy-based devices used in this study are the devices commonly used in stomach cancer surgery with the approval of the Ministry of Food and Drug Safety. The side effects and risks that may occur in this study are expected not to go beyond the range of complications that are expected to occur in stomach cancer operation, not due to the malfunction of the energy-based resection mechanism. Thus, the additional risk of participating in the study by the study participants does not outweigh the risks in general gastric cancer surgery. On the other hand, if energy-based resection devices have different effects on the subjects of clinical studies, it can provide a basis for surgeons to select surgical instruments used for gastric surgery.

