- Complications and mortality rate within 30 days after surgery: Clavien-Dindo classification is used to grade the complications of the three groups and the $\chi 2$ test is performed using the Cross Table for the frequency of complications and Grade IIIa complications. For the total complications, the Student's t test or the ANOVA test was performed using the Comprehensive Comorbidity Index between the three groups.

- After 4 days postoperatively, serum CRP, amylase, serum/ascites triglyceride: The preoperative mean value was used as the baseline and the Student's t test or the ANOVA test was performed on the mean value of the three groups at the 4th postoperative day
- Post-operative pain medication frequency: Student's t test or ANOVA test is performed on the average daily frequency of use among the three groups of non-PCA narcotic analgesics.
- Postoperative visual pain score (VAS score): The mean postoperative VAS score between the three groups is verified by Student's t test or ANOVA test.
- Post-operative transfusion, gas evacuation, liquid diet initiation: If the postoperative Hb < 8, transfusion can be performed under the judgment of the tester and record transfusion. The mean number of days from the day of surgery was verified by Student's t test or ANOVA test among the three groups.
- Length of hospital stay: The average number of days between surgery and discharge is assessed by Student's t test or ANOVA test among the three groups.
- Re-admission, emergency room visit: Within 30 days from the date of surgery, record admission / visit and evaluate complications if you are re-admitted to the hospital or visited the emergency room.
- A new version of the harmonic scalpel was introduced during the research and the target of the ultrasonic group is being studied with a new product. (Since IRB approval in July 2018)
- We will compare the results of the patients who underwent surgery in the ultrasonic group regarding to old instrument versus new instrument. In the comparison between the groups, it will be analyzed whether there is a difference between the inclusion and the non-inclusion of the subject who underwent surgery with the old apparatus. In these ways, it will be notated in the final report whether there is any influence on the results of the study by the change of the device.

9-1) General principles of statistical analysis.

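### Complications and mortality are defined to 30 days after surgery, but the last dated contact falls at POD 19–31 or POD 21–28, and no contact or record check is dated POD 30

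*Combined protocol and SAP*

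**What the plan says.** **Endpoint window.** The secondary endpoint list in Section 11-4)-(2) has "Complication within 30 days after surgery, mortality rate", and the analysis text in Section 11-9)-(2) has "Complications and mortality rate within 30 days after surgery". The same analysis section counts re-admissions and emergency visits over 30 days from surgery. A footnote to the schedule table says "Adverse events are evaluated up to POD # 30".

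**Follow-up, counted from discharge.** Section 11-1) plans that "patients will be discharged during the post-op 5-10 days", with an exception for patients whose adverse reaction calls for a longer admission or further follow-up. It then says "Follow-up will be made until the first out-patient visit after 2-3 weeks of discharge". Section 11-1)-(3) describes complication monitoring as running "from the end of operation to 2-3 weeks after discharge, patients will be monitored to check for complications and mortality before POD 30", and it records reasons for re-admission over that same follow-up period.

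**Follow-up, counted from surgery.** Section 4-4) describes the same visit as "first outpatient visit after discharge (3-4 weeks after surgery".

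**Other relevant text.** After the outpatient-visit column, the schedule table has a last column for study end or early termination. Adverse events are ticked there, but the column has no date. Section 9-1) defines trial completion, for the per-protocol set, as normal discharge. Section 13-3) says the trial adds no outpatient visits. Selection criterion (5) requires that 30-day outpatient follow-up be feasible.

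**The concern.** An endpoint labelled 30-day should rest on a procedure that establishes each patient's status at day 30. Here the stated follow-up rule usually closes before the window does, and two sections give different dates for the closing visit.

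Two things are at stake. First, complications, re-admissions, emergency visits and deaths after the visit may be missed. Section 9-2) analyses observed data only. No rule says whether a patient last seen on, say, POD 22 without an event counts as event-free at 30 days or as incompletely observed, and the planned χ² test on complication frequency needs that distinction.

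Second, when the visit is counted from discharge, a longer stay gives a later last contact. Length of stay is itself a secondary endpoint and could differ by device, and a complication that prolongs the stay also prolongs observation. That opens a route to unequal ascertainment between arms. The surgeon knows the assigned device (Section 11-2)), so late follow-up left to discretion is best avoided.

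**Working it through.** **Inputs.** Discharge on POD 5–10 and a visit 14–21 days after discharge (Sections 11-1) and 11-1)-(3)); the same visit 21–28 days after surgery (Section 4-4)); endpoint window to POD 30 (Sections 11-4)-(2) and 11-9)-(2), schedule footnote). The plan states no figure for completeness of follow-up, so there is none to reproduce.

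**Timing from discharge.** Last dated contact = discharge day + visit delay. Earliest: 5 + 14 = POD 19. Latest: 10 + 21 = POD 31.

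| Discharge (POD) | Earliest contact | Latest contact | Days short of POD 30 |
|---|---|---|---|
| 5 | 19 | 26 | 4 to 11 |
| 6 | 20 | 27 | 3 to 10 |
| 7 | 21 | 28 | 2 to 9 |
| 8 | 22 | 29 | 1 to 8 |
| 9 | 23 | 30 | 0 to 7 |
| 10 | 24 | 31 | 0 to 6 |

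A patient discharged on POD 5–8 cannot have a dated contact at POD 30 or later. Each extra day in hospital moves the last contact by one day.

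**Timing from surgery.** The visit is at POD 21–28. No patient reaches POD 30; the shortfall is 30 − 28 = 2 to 30 − 21 = 9 days. This timing does not depend on length of stay.

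**Share reaching POD 30, discharge-based timing.** The documents give no distribution of discharge day or visit delay. Taking both as uniform and independent, which is an assumption:
- Whole days: 6 × 8 = 48 combinations. Three reach POD 30 (9 + 21, 10 + 20, 10 + 21). 3/48 = 6%, so 45/48 = 94% fall before POD 30. The mean last contact is POD 25, about 5 days short.
- Continuous time: the share reaching POD 30 is (½ × 1 × 1)/(5 × 7) = 0.5/35 = 1.4%, so 98.6% fall before POD 30.

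**Overlap of the two timings.** Of the 48 whole-day combinations, 39 (81%) fall within POD 21–28. The two windows largely agree in range. They differ at the edges and in whether the date follows discharge or surgery.

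**Does other text supply the missing contact?**
- The schedule footnote gives a window but no method or contact.
- The study-end column is undated. Because Section 9-1) ties completion to discharge, it cannot be taken as a POD 30 contact.
- Section 11-9)-(2) states 30-day recording of re-admissions and emergency visits but not how an event after the last visit comes to light. Section 11-1)-(3) ties the same recording to the shorter follow-up period.
- Section 13-3) rules out extra clinic visits, and selection criterion (5) requires feasibility without scheduling anything.

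**The case against.** The strongest reply is that a last dated visit is not the same as a last observation. The protocol states 30-day capture more than once: in the schedule footnote, in the rule for re-admissions and emergency visits, and in the monitoring sentence of Section 11-1)-(3), which names POD 30 as well as the shorter period. The study-end column also ticks adverse events after the outpatient visit. This stands to the following extent: a reader might infer that most patients are not observed for 30 days, and the documents do not show that. They show that no dated contact covers POD 30 and that no method is specified. The Section 11-1)-(3) sentence is ambiguous and is not an explicit limit on monitoring.

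A reader might also infer that a device which shortens stay would look safer for that reason alone. That goes too far. Dependence on stay arises under Sections 11-1) and 11-1)-(3), not under Section 4-4), and the documents give neither an expected difference in stay between arms nor event-time data. Patients kept in hospital for an adverse reaction are also outside the POD 5–10 rule, so the arithmetic describes the uncomplicated course.

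The percentages depend on an assumed distribution and count a visit on POD 28 or 29 as short. They describe contact dates, not lost events.

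None of this supplies a contact or check at POD 30, or removes the conflict between the two visit timings.

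**Conclusion.** The concern holds in this form. The endpoint window is 30 days, the stated follow-up rule ends at a visit on POD 19–31 or POD 21–28 depending on the section, the two timings contradict each other, and nothing dated covers POD 30 although the protocol intends to. The date ranges, and the finding that discharge on POD 5–8 cannot lead to contact at POD 30, follow from the text without further assumption. The 94% figure (98.6% in continuous time) and the average shortfall of about 5 days rest on uniform, independent timings.

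Late events may be under-counted; the documents do not establish that they are, and the loss cannot be sized. Differential ascertainment is possible under the discharge-based timing only. These are secondary and safety endpoints, and CRP at POD 2 is not touched. The plan should be corrected, but the main comparison is not threatened.

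**What to change.** 1. Reconcile Sections 11-1), 11-1)-(3), 4-4) and 11-9)-(2) and the schedule footnote to a single ascertainment window counted from surgery, and date the study-end column or say what it represents.
2. For every patient, record complication, re-admission, emergency-visit and vital status through POD 30, by a record check or brief telephone call. A check limited to the trial hospitals' records could miss events treated elsewhere; a call would cover those.
3. State in the SAP how a patient without confirmed status to POD 30 enters the complication analysis, and report by arm how many have confirmed status.
4. If POD 30 status cannot be obtained, rename the endpoint to the period actually observed.

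The cost is a small amendment and one short status check for each of up to 189 patients, all of whom must already be available for 30 days. Version 2.1 is dated July 2021, and Section 11-9)-(2) describes a device change during the study with approval in July 2018, so new visit timing could reach only later patients. For those already treated, a record check is the practical route.
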